Cooking Class/Demonstration Evaluation – At the conclusion of the cooking classes for the intervention group and the cooking demonstrations for the control group there will be a class evaluation given to assess participants’ impressions of the classes or demonstrations. This evaluation will be available on the study website, and participants will have time in class to complete the evaluation and can do so on their smart phone or tablet. Participants will also have the option to complete this evaluation at a later time on their home computer.

Intervention

Participants in both treatment and control groups will attend weekly sessions of the behavioral weight loss program. Sessions will be 1 hour long and will include a weekly lesson as well as a group discussion. These sessions will be standalone meetings (1 hour) every other week for 24 weeks and paired with the cooking class biweekly (2 hours). Weight loss meetings and cooking classes will occur in the same space.

Every week participants will be asked to track their food, exercise, and weight every day. The tracking will be done through My Fitness Pal and reviewed by the group facilitator on a weekly basis in order to offer individualized feedback to participants. Participants will be asked to complete short weekly homework assignments that relate to the week’s lesson. Homework will also be reviewed by the group facilitator.

Facilities and Equipment Needed

Cooking Labs – The cooking classes and demonstrations will take place in the Nutrition and Food Sciences teaching kitchen located in the Marsh Life Science building. The teaching kitchen has room for 16 students to complete hands on cooking labs, and an additional space where students can get directions, eat, and watch cooking demos. The kitchens are fully stocked with the necessary kitchen equipment.

Follow-up Data Collection

Participants will be alerted prior to their follow-up assessment appointment to complete the online questionnaires which are anticipated to take approximately 30 minutes to complete and 3 days of the ASA24 (less than 30 minutes per day). They will also be scheduled to come into the research office to get weighed, at which time the weight loss achieved will be recorded.

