Hypothesis 2: Food agency, cooking perceptions and cooking frequency will be significantly greater in the COOKING versus DEMONSTRATION conditions at 12 and 24 weeks.

Analysis Aims 1 and 2: The first and second hypotheses will be addressed using a repeated measures analysis of variance with treatment condition as the between group factors and assessment time as the within subject factor recalling that the baseline value will be subtracted from all subsequent values. An intent-to-treat approach will be used as the definitive analysis perspective for both the primary hypothesis testing and the secondary analysis of data. The use of a multiple imputation process will be conducted if the missing data can be assumed to be missing at random or completely at random. The intent-to-treat approach will require the use of a mixed model approach that can deal with repeated measures data and which can also deal with missing data (e.g. SAS ProcMixed or BMDP5V)

Aim 3: To explore the feasibility and acceptability of adding cooking classes to a standard behavioral weight loss intervention.

Analysis Aim 3: Feasibility and acceptability will be monitored by evaluating attendance and self-monitoring as well as qualitative data related to the perceived usefulness of the cooking classes or demonstrations.

Risks/Benefits: *Describe any potential or known risks. This includes physical, psychological, social, legal or other risks.*

Estimate the probability that given risk may occur, its severity and potential reversibility. If the study involves a placebo or washout period, the risks related to these must be addressed in both the protocol and consent. Describe the planned procedures for protecting against or minimizing potential risks and assess their likely effectiveness. Where appropriate, discuss plans for ensuring necessary medical or professional intervention in the event of adverse effects to the subjects. Discuss the potential benefits of the research to the subjects and others. Discuss why the risks to the subjects are reasonable in relation to the anticipated benefits to subjects and others. Discuss the importance of the knowledge gained or to be gained as a result of the proposed research and why the risks are reasonable in relation to the knowledge that reasonably may result. If there are no benefits state so.

Potential Risks.

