Vulnerable Populations: Explain the rationale for involvement of special classes of subjects, if any. Discuss what procedures or practices will be used in the protocol to minimize their susceptibility to undue influences and unnecessary risk (physical, psychological, etc.).

Not applicable

Number of Subjects: What is the anticipated number of subjects to be enrolled at UVM/UVM Medical Center and in the case of a multi-center study, with UVM/UVM Medical Center as the lead, the total number of subjects for the entire study.

This is a pilot study with no previous data available to calculate expected statistical power. The sample size chosen was practical as our foods lab can only accommodate 16 people at a time. Two waves of each intervention arm would give us data on approximately 64 subjects. This preliminary data will be used to determine the sample size power needed for a larger study with sufficient statistical power.

Inclusion/Exclusion Criteria: Eligibility and ineligibility criteria should be specific. Describe how eligibility will be determined and by whom. Changes to the eligibility criteria at a later phase of the research have the potential to invalidate the research.

To be eligible to participate, participants must be at least 18 years old and have a Body Mass Index (BMI) between 25-50 kg/m². Review of previous research studies conducted by this research groups has found that individuals with a BMI greater than 50 do not have success with the planned intervention. These individuals require a more intensive approach to see a

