reduction in weight than what they study intervention offers. Individuals must also be free of medical problems that might contraindicate participation in a behavioral weight loss program containing an exercise component, not currently on medication that might affect weight loss, and not enrolled in another weight reduction program (all of which would be problematic confounds for the primary outcome of body weight). Participants will also be excluded if they are pregnant, plan to become pregnant in the next six month, or are lactating as these would be problematic confounds for the primary outcome of body weight. Additionally, weight loss is not generally recommended for pregnant women and when it is must be closely monitored by a physician. Participants will not be eligible if they are currently cooking (from scratch) more than 3 meals at home per week. All participants must have a computer with Internet access (at home or work) in order to track their diet and exercise behaviors. Participants must also agree to be randomized to either of the study arms and be available for both scheduled meeting times.

Inclusion of Minorities and Women: Describe efforts to include minorities and women. If either minorities or women are excluded, include a justification for the exclusion.

Women and minorities will be included. Women are more likely to participate in weight loss interventions than men.

Inclusion of Children: Describe efforts to include children. Inclusion is required unless a clear and compelling rationale shows that inclusion is inappropriate with respect to the health of the subjects or that inclusion is inappropriate for the purpose of the study. If children are included, the description of the plan should include a rationale for selecting or excluding a specific age range of children. When included, the plan must also describe the expertise of the investigative team in working with children, the appropriateness of the available facilities to accommodate children, and the inclusion of a sufficient number of children to contribute to a meaningful analysis relative to the purpose of the study. If children are excluded then provide appropriate justification. Provide target accrual for this population.

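### The planned model treats classmates as independent, although treatment is delivered in what appear to be four classes; any positive class-specific correlation makes the between-arm test reject too often

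*Combined protocol and SAP*

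**What the plan says.** **Delivery.** Study Design randomises individuals, in two waves of 32, to two arms. Both arms receive 24 weekly group weight-loss sessions. One arm adds 12 hands-on cooking classes and the other 12 cooking demonstrations. The Intervention section says of the weekly sessions: "Sessions will be 1 hour long and will include a weekly lesson as well as a group discussion". It adds: "Weight loss meetings and cooking classes will occur in the same space". The Cooking Program places the classes after the weight-loss meetings and has COOKING participants work in pairs. The same chef leads the sessions in both arms, and Study Design gives both arms the same counselor-delivered elements.

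**Class size.** Facilities and Equipment Needed states: "The teaching kitchen has room for 16 students to complete hands on cooking labs". Number of Subjects explains the sample size by the fact that "our foods lab can only accommodate 16 people at a time", and continues: "Two waves of each intervention arm would give us data on approximately 64 subjects". Inclusion/Exclusion Criteria adds: "Participants must also agree to be randomized to either of the study arms and be available for both scheduled meeting times".

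**Analysis.** Hypotheses 1 and 2 predict a significant advantage for COOKING at 12 and 24 weeks. Analysis Aims 1 and 2 tests this with a "repeated measures analysis of variance with treatment condition as the between group factors and assessment time as the within subject factor" on change from baseline. It calls for a mixed model, for two stated reasons: repeated measures and missing data. The documents contain no class, wave or team term, no ICC, no design effect and no cluster-robust variance. They also state no significance level and plan no confidence intervals.

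**The concern.** People who spend months in the same room, discussing their progress and cooking together, may come to resemble one another in outcome. Where that resemblance is specific to a class, it does not average out over participants as independent variation does. It averages out only over classes, and there appear to be two per arm. A lively or a flat group in one class could then pass as an effect of cooking.

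A model with condition and time alone computes its standard error as if about 64 independent people had been observed. Under positive class-specific correlation that standard error is too small, and a claim of significance carries more than its nominal error.

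The same omission affects the pilot's onward use. Number of Subjects says that the data will set the sample size of a larger trial. A calculation from person-level variances alone would leave any clustering out.

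**Working it through.** **1. Reproduce the plan's figure.** 16 places × 2 waves × 2 arms = 64, which matches the stated total. So one class of about 16 per arm per wave, four in all, is the natural reading. It remains an inference.

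**2. Formula.** Let *m* be the number per class and ICC the correlation between classmates that is specific to their class. Relative to independence, the variance of the arm difference is multiplied by 1 + (*m* − 1) × ICC. The standard error (SE) is therefore understated by about √(1 + (*m* − 1) × ICC). The true error of a nominal two-sided 5% test is about 2 × [1 − Φ(1.96 / factor)]. If only the COOKING classes cluster, half of the variance is inflated and the factor is √(1 + (*m* − 1) × ICC / 2).

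**3. Inputs.** *m* = 16 comes from the documents. Assumed: the two-sided 5% level, ICCs of 0.01, 0.02 and 0.05, and *m* = 13 for about 20% dropout.

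**4. Results.**

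| ICC | SE factor, both arms, *m* = 16 | True error | SE factor, COOKING only, *m* = 16 | True error | SE factor, both arms, *m* = 13 | True error |
|---|---|---|---|---|---|---|
| 0 | 1.00 | 5.0% | 1.00 | 5.0% | 1.00 | 5.0% |
| 0.01 | √1.15 = 1.07 | 6.8% | √1.075 = 1.04 | 5.9% | √1.12 = 1.06 | 6.4% |
| 0.02 | √1.30 = 1.14 | 8.6% | √1.15 = 1.07 | 6.8% | √1.24 = 1.11 | 7.8% |
| 0.05 | √1.75 = 1.32 | 13.8% | √1.375 = 1.17 | 9.5% | √1.60 = 1.26 | 12.1% |

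**5. Check by simulation.** Two arms × two waves were simulated at weeks 12 and 24, with an assumed within-person correlation of 0.7, complete data and 60,000 runs per setting. With both arms clustering and *m* = 16, the week-24 error was 5.0%, 6.8%, 8.4% and 14.3% at ICC 0, 0.01, 0.02 and 0.05. The overall condition effect was slightly worse at the positive ICCs: 7.2%, 9.1% and 15.7%.

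**6. What both arms of a wave share.** A wave effect common to both arms cancels from their difference. With a classmate correlation of 0.05 wholly shared by a wave's two arms, the simulated error was 4.9%. With half shared, it was 9.3%.

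**7. Does a wave term cure it?** No. With wave as a fixed effect, the simulated errors were 6.8%, 8.7% and 14.3%.

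**8. Does multiplying the SE help?** Yes, if the assumed ICC is right and equal in both arms: the error returns to 5.0% to 5.1% without a wave term. If only COOKING clusters, the multiplier over-corrects, and a one-time-point simulation gave 4.3%, 3.8% and 2.8%.

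**9. Could a class-level test replace it?** Four class means less two arm means leave 2 degrees of freedom (critical *t* 4.30), or 1 with wave fixed (12.7). The person-level test has 62 (2.00). A class-level test is valid but would detect almost nothing.

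**The case against.** - **The trial is individually randomised, and the plan subtracts baseline.** Both are true, and both help balance people at entry. Neither prevents outcomes from correlating after months in one class.
- **The chef and the counselor-delivered elements are common to both arms.** This removes some sources of class difference. Peer influence, group discussion and meeting time remain.
- **The weekly meetings may not be split by arm.** This stands. The shared space and the order of sessions suggest a split, but the documents do not state one. The requirement to be available at both meeting times fits a split but does not prove it. If a wave's arms met together, that part of the correlation would cancel.
- **COOKING may cluster more than DEMONSTRATION.** This also stands, since only COOKING participants work in pairs. The equal-ICC figures are then too high. Weekly discussion could cluster both arms, so clustering in COOKING alone is a lower bound for a given ICC, not a prediction. Correlation within pairs was not modelled.
- **It is a pilot.** The protocol says so: "This is a pilot study with no previous data available to calculate expected statistical power". Its p-values should carry little weight in any case. Yet the hypotheses are worded in terms of significance, and the analysis section speaks of primary hypothesis testing.

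A reader might infer that the error rate will be 14%, or that the plan's confidence intervals are too narrow. The documents support neither: they give no ICC, and they plan no intervals. Nor do they make this a cluster-randomised trial.

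**Conclusion.** The concern holds in conditional form. The plan omits a class structure that its own logistics imply. With any positive class-specific correlation, the person-level standard error is too small and the test of COOKING superiority rejects too often. An exception would be a shared wave variance more than about 30 times the class variance, which is unlikely.

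Under the stated assumptions (two-sided 5%, 16 per class), the true error is about 7%, 8.5% and 14% at ICC 0.01, 0.02 and 0.05 when both arms cluster equally. It is about 6%, 7% and 9.5% when only COOKING does. It is 5% when there is no class-specific correlation. Which of these applies cannot be learned from the documents, and four classes will barely inform it. The point should be fixed because it bears on what the trial may conclude and because the remedy is cheap. Confidence is medium: the group delivery and the missing term are documented, but the size of the effect is not.

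**What to change.** In Analysis Aims 1 and 2:

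1. Record class and wave for each participant, and state whether the weekly meetings are held separately by arm.
2. For each outcome, report the between-arm difference with a 95% confidence interval at week 24, and at week 12 where the outcome is collected then. The week-12 schedule must first be reconciled. The opening summary gives assessments at baseline and week 24, and Procedures gives questionnaires at baseline and study end. Study Design has 0, 3 and 6 months, and the hypotheses name 12 and 24 weeks.
3. Beside each interval, give sensitivity intervals with the standard error multiplied by √(1 + (*m* − 1) × ICC), at pre-stated ICCs such as 0.01, 0.02 and 0.05. Here *m* is the average number per class in that analysis. State that this assumes the same ICC in both arms and is conservative if only one arm clusters.
4. State that between-arm p-values are exploratory, and that no claim of significance will rest on the unadjusted person-level p-value, because four classes leave only 1 to 2 degrees of freedom for a class-level test.
5. Report class-level means, and carry a design effect over a range of ICCs into the sample size of the larger study named in Number of Subjects.

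**Cost.** Protocol wording and a few lines of code, with no added participants or procedures. With 16 per class the sensitivity intervals are 7%, 14% and 32% wider at the three ICCs, and significance claims are softer. The intervals show how fragile the result is to an assumed ICC. They cannot show whether clustering occurred.

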Overweight and obese but otherwise healthy participants (n=64) will be recruited using online postings on local Front Porch Forum sites, the University of Vermont's weekly announcement newsletter (research studies), and the University of Vermont Medical Center's wellness calendar. Additionally, physical posters will be posted around UVM's campus, UVMMC's campus, and local physician's offices who agree to display posters. We will also draw from a running waitlist of interested weight loss participants held by the Nutrition and Food Sciences Department. Recruitment and study initiation will occur in two waves. Wave 1 aims to recruit 32 individuals who will then be randomized to 1) a 24 week, 24 session group behavioral weight loss intervention with 12 bi-weekly cooking lessons; or, 2) the same 24 week, 24 session group behavioral weight loss intervention with 12 bi-weekly cooking demonstrations. Both groups get the same intervention and the same counselor delivered intervention elements; the presence of active cooking lessons vs. passive observed cooking demonstrations is the only difference between conditions. Assessments will be conducted at 0, 3 and 6 months. Wave 2 (n=32) will follow the same process as Wave 1 approximately two months after Wave 1 is initiated.

To be eligible to participate, individuals must be at least 18 years old and overweight or obese (have a Body Mass Index (BMI) 25-50 kg/m²). Individuals must also be free of medical problems that might contraindicate participation in a behavioral weight loss program containing an exercise component, not currently on medication that might affect weight loss, not pregnant or lactating, not enrolled in another weight reduction program and not currently cooking more than 3 meals at home per week. All participants must have a computer with Internet access (at home or work) in order to track their diet and exercise behaviors. Participants must also agree to be randomized to either of the study arms.

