Group assignments will be determined by a random assignment table created by the UVM Medical Biostatistics department using PROC PLAN in SAS. The program will stratify (arrange) groups so that they are statistically similar in distribution of both gender and weight classification (BMI<30 and BMI≥30). This program will allow study personnel to access a series of envelopes that will tell them which group the participant is assigned to. A participant ID number will be permanently associated with the participant to identify which group they have been assigned to. To avoid differential impact of and to assure equal representation in each group, eligible subjects will be stratified by BMI and gender. To minimize loss to follow up, standardized training of staff will be provided focusing on rapport building, motivational interviewing and problem solving. Participants will be educated on the importance of follow up and detailed contact information is obtained at study initiation.

The Behavioral Weight Loss Program: We have developed and implemented a theory-based group-delivered behavioral weight control program in two previous studies that incorporates the elements of current thinking and empirical data on successful weight loss programs,³⁷⁻³⁹ including restricted calorie intake and increased physical activity. Key behavioral strategies to facilitate making sustained changes in dietary habits and activity patterns are introduced, promoted and reinforced throughout the program. In-person sessions facilitated by an interventionist provide the group meetings. The program provides 24 weekly facilitated group sessions over 6 months. Target weight losses of 10% of baseline weight are promoted. Behavioral strategies are drawn from social cognitive theory⁴⁰ and self-regulation theory⁴¹ and mirror the core components incorporated into such successful programs as Look AHEAD.⁴² In addition to attending weekly classes, participants will track their food intake, exercise, and weight. They will share their online tracking diaries with the group facilitator who will offer individualized feedback on their progress.

The Cooking Program

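### Participants are randomised in two waves about two months apart, but the Aims 1 and 2 model omits wave; adding it buys a small gain in precision at almost no cost

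*Combined protocol and SAP*

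**What the plan says.** Study Design sets out the enrolment: "Wave 1 aims to recruit 32 individuals who will then be randomized to" one of the two arms, and "Wave 2 (n=32) will follow the same process as Wave 1 approximately two months after Wave 1 is initiated". The same section describes how assignments are made and says that "eligible subjects will be stratified by BMI and gender"; wave is not listed as a stratum.

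Number of Subjects explains the total. It notes that "our foods lab can only accommodate 16 people at a time" and that "Two waves of each intervention arm would give us data on approximately 64 subjects". It also states that "This is a pilot study with no previous data available to calculate expected statistical power", and that the data will be used to size a larger study.

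Statistical Considerations, under Analysis Aims 1 and 2, specifies a repeated measures analysis with "treatment condition as the between group factors and assessment time as the within subject factor", applied to values with baseline subtracted. A mixed model is to handle the repeated measures and missing data, with multiple imputation where its assumptions are met. No covariates are named. Wave appears only in the design and sample-size text and never in the analysis.

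**The concern.** Each wave is recruited and then randomised, so wave is a block within which allocation takes place. It also fixes the calendar dates on which a participant reaches weeks 12 and 24. If the two waves differ in average change in weight, diet quality or cooking frequency, a model without wave treats that difference as unexplained person-to-person variation.

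Two things are at stake. The first is precision: the interval for the arm difference is wider than it need be, and the variance estimate the pilot passes to the larger study is too high. The second arises only if the arms are unequally represented in the two waves among those analysed. Part of the wave difference then moves into the estimated arm difference.

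**Working it through.** **Inputs from the documents.** Wave size 32, two waves, two arms (Study Design); 16 places in the kitchen (Number of Subjects; Facilities and Equipment Needed). The plan's total reproduces: 16 × 2 arms × 2 waves = 64. There is no power calculation, effect size or SD to reproduce.

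**Assumptions.** Within-cell SD of change = 1, one visit, two-sided 5% level. The gap g is the difference between waves in mean change from baseline, in SD units, and is the same in both arms. The documents give no value for g, so 0.25, 0.5 and 1.0 are shown. A constant wave difference in starting level cancels when baseline is subtracted and does not enter g.

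**Precision with 16 in every cell.** Without wave, the expected residual variance is 1 + (g²/4) × 64/62.

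- g = 0.25: 1 + 0.015625 × 1.0323 = 1.016
- g = 0.5: 1 + 0.0625 × 1.0323 = 1.065
- g = 1.0: 1 + 0.25 × 1.0323 = 1.258

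The half-width with wave is t(0.975, 61) × √(4/64) = 1.9996 × 0.25 = 0.4999. Without wave it is t(0.975, 62) × √(variance × 4/64), where t = 1.9990.

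| g (SD) | Variance too high by | Half-width without wave | Ratio to 0.4999 | True coverage without wave |
|---|---|---|---|---|
| 0.25 | 1.6% | 0.5038 | 1.008 | 95.2% |
| 0.5 | 6.5% | 0.5156 | 1.031 | 95.7% |
| 1.0 | 26% | 0.5605 | 1.121 | 97.2% |

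Coverage uses the fact that the residual sum of squares without wave is noncentral chi-square with 62 degrees of freedom and noncentrality 16g², while the arm difference keeps its true variance of 4/64. Coverage above 95% means the test is conservative.

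A true difference of 0.71 SD gives 80% power with wave in the model. Without wave, power is about 80%, 78% and 73% for the three gaps. The detectable difference at 80% power is 0.71 SD on either 61 or 62 degrees of freedom, so the adjustment costs essentially nothing if g is zero.

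**Shift in the arm difference.** Size of shift = |wave-2 share in COOKING − wave-2 share in DEMONSTRATION| × g. Cells below are wave 1/wave 2, COOKING then DEMONSTRATION.

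- 16/16 and 16/16: |0.5 − 0.5| × g = 0, whatever g is.
- 16/14 and 14/16 (unfilled seats): |14/30 − 16/30| × 0.5 = 0.067 × 0.5 = 0.03 SD.
- 16/12 and 12/16 (completers after uneven dropout): |12/28 − 16/28| × 0.5 = 0.143 × 0.5 = 0.07 SD.

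The last two need an imbalance that the plan does not intend. It remains possible because wave is not a listed stratum and balance rests on the 16-seat limit.

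**The case against.** The strongest case against is that little follows from the omission. At gaps of 0.25 and 0.5 SD the interval is only about 1% and 3% wider. Nothing in the documents supports a full-SD gap between two cohorts receiving the same programme. The documents do not mention season; it is an inference from the two-month lag, and two 24-week periods starting about 9 weeks apart overlap for about 15 weeks. The error is in the safe direction, and this is a pilot. All of that stands, and it is why the point is minor. It does not argue for leaving wave out, since the adjustment is nearly free and the pilot's variance is meant to size the next trial.

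A reader might infer that leaving out wave biases the arm comparison or raises the false-positive rate. The documents do not support either at the planned 16 per cell: the shift is exactly zero and coverage is at or above 95%. Nor can one illustrate bias with, say, 18 enrolled in one arm of a wave, because 18 people do not fit in a kitchen for 16.

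A further objection is that adding wave could make matters worse if each arm-by-wave cell meets as one class. Correlation within classes makes intervals too narrow, and removing wave variance narrows them further. In 40,000 simulated trials per setting (16 per cell, g = 0.5), type I error rose from about 6% without wave to about 7% with it at an assumed intraclass correlation of 0.01, and from about 13% to about 14% at 0.05. This is fair as a warning about how to read the adjusted interval. But nearly all of the excess comes from the class correlation, which is a separate matter; an unmodelled wave effect is not a sound remedy for it.

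Finally, the analysis text is a short narrative that does not forbid covariates, and it also omits the declared strata, gender and BMI class. That is true, but adding those two would still leave wave out.

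**Conclusion.** The point holds as a small, nearly free gain in precision. The model does not reflect the two-wave randomisation in Study Design. At the planned cell sizes the consequence is an inflated residual variance and a conservative test: intervals about 0.8%, 3.1% and 12% wider, and a variance about 1.6%, 6.5% and 26% too high, for assumed gaps in change of 0.25, 0.5 and 1.0 SD. The lower two are the more plausible.

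Bias is confined to underfilled groups or to dropout that differs by arm and wave. It is about 0.03 to 0.07 SD at a 0.5 SD gap in the cases worked above. These sizes rest on the assumed gaps, a common within-cell SD, a single visit and no correlation within classes.

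**What to change.** In Statistical Considerations, Analysis Aims 1 and 2, add wave and wave-by-assessment-time as fixed effects in the mixed model for every Aim 1 and Aim 2 outcome, and report the arm difference averaged over waves. Include wave in any multiple imputation model. Use the residual variance from this model when sizing the larger study.

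The cost is a sentence or two of analysis wording and one degree of freedom per visit (62 to 61 in the single-visit case), with no new data and no change to conduct. Naming wave now also avoids a discretionary choice after the data are seen.

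This change does not deal with correlation within class groups. The plan should address that separately, so that the narrower wave-adjusted interval is not overread.
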